Grade 2	If everolimus is interrupted/discontinued, ribociclib should also be interrupted/discontinued. Resume ribociclib at same dose level if everolimus is resumed at same or lower dose.	If toxicity is tolerable, no dose adjustment required Initiate appropriate medical therapy and monitor. If toxicity becomes intolerable, interrupt dose until recovery to Grade ≤ 1. Re-initiate everolimus at same dose level. If the same toxicity recurs at grade 2, interrupt everolimus until recovery to grade ≤ 1 and re-initiate treatment at lower dose level (50% of previous dose).

Worst toxicity (CTCAE 4.03 Grade)*	Regimen Modifications for Ribociclib Management Recommendations	Regimen Modifications for Everolimus Management Recommendations
Grade 3	If everolimus is interrupted/discontinued, ribociclib should also be interrupted/discontinued. Resume ribociclib at same dose level if everolimus is resumed at lower dose.	Dose interruption until recovery to grade ≤ 1. Initiate appropriate medical therapy and monitor. Re-initiate everolimus at the next lower dose level (50% of previous dose). If toxicity recurs at grade 3, discontinue treatment study.
Grade 4	Discontinue ribociclib+everolimus	Discontinue everolimus and treat with appropriate medical therapy.

Severity Description: 1 = mild symptoms; 2 = moderate symptoms; 3 = severe symptoms; 4 = life-threatening symptoms

* Common Terminology Criteria for Adverse Events (CTCAE) version 4.03. All dose modifications should be based on the worst preceding toxicity.

** If Grade 3 or 4 hyperbilirubinemia is due to the indirect (non-conjugated) component only, and hemolysis as the etiology has been ruled out as per institutional guidelines (e.g., review of peripheral blood smear and haptoglobin determination), then continue treatment at the discretion of the Investigator.

***LFTs include albumin, ALT, AST, total bilirubin (fractionated if total bilirubin > 2.0 x ULN), alkaline phosphatase and GGT.

If dose reduction is required, the suggested dose is approximately 50% lower than the previously administered dose.

Ribociclib dose adjustment and management recommendation for ILD/pneumonitis (CTCAE v4.03)

Grade	Dose Adjustment and Management Recommendations
1 (asymptomatic)	No dose adjustment required. Initiate appropriate medical therapy and monitor as clinically indicated.
2 (symptomatic)	Interrupt ribociclib dose until recovery to Grade ≤1, then resume ribociclib at the next lower dose level*.
3 and 4 (severe)	Discontinue ribociclib

* An individualized benefit-risk assessment should be performed before resuming ribociclib

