Grade 1 (> ULN and ≤ 1.5 x ULN)	Maintain dose level with liver function test (LFTs)*** monitored as per protocol Confirm at 48-72 hours later	Continue regimen
Grade 2 (> 1.5 and ≤ 3.0 x ULN) with ALT or AST ≤ 3.0 x ULN	Dose interruption of ribociclib If resolved to ≤ grade 1 in ≤21 days, then maintain dose level. If resolved to ≤ grade 1 in >21-28 days or toxicity recurs, then reduce 1 dose level. Repeat liver enzymes and bilirubin tests twice weekly for 2 weeks after dose resumption. If toxicity recurs after 1 dose reduction, or recovery to < grade 1 in > 28 days, discontinue ribociclib+everolimus.	If ribociclib is interrupted/discontinued, everolimus should also be interrupted/discontinued. Resume everolimus at same dose level if ribociclib is resumed at either the same or lower dose. If toxicity recurs after 1 dose reduction, or recovery to ≤ grade 1 in > 28 days, discontinue ribociclib+everolimus.
Grade 3 (> 3.0 and ≤ 10.0 x ULN) with ALT or AST ≤ 3.0 x ULN	Dose interruption of ribociclib, until resolved to ≤ grade 1, then lower 1 dose level of ribociclib Repeat liver enzyme and bilirubin tests twice weekly for 2 weeks after dose resumption If resolved to ≤ grade 1 in > 28 days or toxicity recurs, discontinue ribociclib+everolimus	If ribociclib is interrupted/discontinued, everolimus should also be interrupted/discontinued. Resume everolimus at same dose level if ribociclib is resumed at lower dose level. If toxicity recurs after 1 dose reduction, or recovery to ≤ grade 1 in > 28 days, discontinue ribociclib+everolimus.
Grade 4 (> 10.0 x ULN)	Permanently discontinue patient from ribociclib+everolimus	
Confounding factors and/or alternative causes for increase of total bilirubin should be excluded before dose interruption/reduction. They include but are not limited to: evidence of liver metastases, evidence of obstruction, such as elevated ALP and GGT typical of gallbladder or bile duct disease, hyperbilirubinemia due to the indirect component only (i.e. direct bilirubin component ≤ 1 x ULN) due to hemolysis or Gilbert Syndrome, other pharmacologic treatment, viral hepatitis, alcoholic or autoimmune hepatitis, other hepatotoxic drugs. For patients with Gilbert Syndrome, these dose modifications apply to changes in direct bilirubin only. Bilirubin will be fractionated if elevated.		

Worst toxicity (CTCAE 4.03 Grade)*	Regimen Modifications for Ribociclib Management Recommendations	Regimen Modifications for Everolimus Management Recommendations

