AST or ALT		
AST or ALT without bilirubin elevation >2 x ULN		
Same grade as baseline or increase from baseline grade 0 to grade 1 (confirmed 48 to 72 hours later)	Maintain dose level with LFTs*** monitored per protocol if same grade as baseline or bi-weekly in case of increase from baseline grade 0 to 1.	Continue regimen
Increase from baseline grade 0 or 1 to Grade 2 (> 3.0 and ≤ 5.0 x ULN)	Dose interruption of ribociclib: If resolved to ≤ baseline value in ≤ then 21 days, then maintain dose level If resolved to ≤ baseline value in > then 21 days or toxicity recurs, then reduce 1 dose level of ribociclib. Repeat liver enzymes and bilirubin tests twice weekly for 2 weeks after dose resumption. If toxicity recurs after 1 dose reduction or recovery to ≤ baseline value is >28 days, discontinue ribociclib+everolimus.	If ribociclib is interrupted/discontinued, everolimus should also be interrupted/discontinued. Resume everolimus at same dose level If toxicity recurs after 1 dose reduction, or recovery to ≤ grade 1 in > 28 days, discontinue ribociclib+everolimus.
Increase from baseline grade 0 or 1 to grade 3 (> 5.0 – 20.0 x ULN)	Dose interruption of ribociclib until resolved ≤ baseline value then reduce 1 dose level of ribociclib. Repeat liver enzymes and bilirubin tests twice weekly for 2 weeks after dose resumption. If toxicity recurs after 1 dose reduction or recovery to ≤ baseline value is >28 days ribociclib+everolimus.	If ribociclib is interrupted/discontinued, everolimus should also be interrupted/discontinued. Resume everolimus at same dose level if ribociclib is resumed at either the same or lower dose. If toxicity recurs after 1 dose reduction, or recovery to ≤ grade 1 in > 28 days, discontinue ribociclib+everolimus.
Increase from baseline grade 2 to grade 3 (> 5.0 – 20.0 x ULN)	Dose interruption of ribociclib until resolved to ≤ baseline grade, then lower 1 dose level of ribociclib Repeat liver enzyme and bilirubin tests twice weekly for 2 weeks after dose resumption If toxicity recurs after 1 dose reduction or recovery to ≤ baseline grade is > 28 days, discontinue ribociclib+everolimus.	If ribociclib is interrupted/discontinued, everolimus should also be interrupted/discontinued. Resume everolimus at same dose level if ribociclib is resumed at either the same or lower dose. If toxicity recurs after 1 dose reduction, or recovery to ≤ grade 1 in > 28 days, discontinue ribociclib+everolimus.

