6.2.3.2 Guidelines for the follow-up of laboratory liver abnormalities

In patients with any clinically relevant laboratory liver abnormality, as defined below, hepatic toxicity monitoring must include **ALL** of the following liver function tests (LFTs): albumin, ALT, AST, total bilirubin (fractionated if total bilirubin $> 2.0 \times$ ULN), indirect bilirubin, alkaline phosphatase (fractionated if alkaline phosphatase is grade 2 or higher), creatine kinase, prothrombin time (PT) or INR and GGT. Note: for patients with Gilbert Syndrome, total and direct bilirubin must be monitored, but intensified monitoring applies to changes in direct bilirubin only. (See Table 12) In case of any occurrence of ALT/AST/total bilirubin increase to grade 2 the LFTs must be monitored weekly (or more frequently if clinically indicated) until the event resolves to \leq grade 1. Thereafter monitoring must be continued every 2 weeks (or more frequently if clinically indicated) for two additional cycles (e.g. 6 weeks). If there is no recurrence of \geq grade 2 ALT/AST/total bilirubin elevations during this period, subsequent monitoring must be performed every 3 weeks.

In case of any occurrence of ALT/ AST/ bilirubin increase to grade 3 or 4, LFTs must be monitored weekly (or more frequently if clinically indicated) until the event resolves to \leq grade 1. Thereafter monitoring must be continued every 2 weeks (or more frequently if clinically indicated) for four additional cycles (e.g. 12 weeks). If there is no recurrence of \geq grade 2 ALT/AST/total bilirubin elevations during this period, subsequent monitoring must be performed every 3 weeks.

Patients who discontinue ribociclib+everolimus treatment due to liver toxicity must be monitored weekly (or more frequently if clinically indicated) until the event resolves to \leq grade 1 or stabilization occurs (no CTCAE grade change over 3 weeks). (See Table 12)

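### Table 11, AST/ALT rows: the two drug columns set different 28-day recovery criteria for stopping both drugs, section 6.2.1 resumes on its own criterion, and individual rows contain gaps, overlaps and one true conflict

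*Combined protocol and SAP*

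**What the plan says.** Table 11 in section 6.2.3 gives each toxicity a ribociclib column and an everolimus column. Three AST/ALT rows (without bilirubin elevation) matter here.

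- **Baseline grade 0 or 1 to grade 2.** The ribociclib column reads "If toxicity recurs after 1 dose reduction or recovery to ≤ baseline value is >28 days, discontinue ribociclib+everolimus". The everolimus column reads "If toxicity recurs after 1 dose reduction, or recovery to ≤ grade 1 in > 28 days, discontinue ribociclib+everolimus". The everolimus column also carries a coupling sentence: "If ribociclib is interrupted/discontinued, everolimus should also be interrupted/discontinued". On dose reduction the ribociclib column says "If resolved to ≤ baseline value in > then 21 days or toxicity recurs, then reduce 1 dose level of ribociclib".
- **Baseline grade 0 or 1 to grade 3.** The same pair of criteria appears. In the protocol text as I have it, the ribociclib stop sentence gives the 28-day condition and the two drug names but no verb.
- **Baseline grade 2 to grade 3.** The ribociclib column says "Dose interruption of ribociclib until resolved to ≤ baseline grade, then lower 1 dose level of ribociclib", with its 28-day stop tied to baseline grade. The everolimus column again ties the stop of both drugs to grade 1 or lower.

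The parallel bilirubin grade 2 row closes its reduction window: "If resolved to ≤ grade 1 in >21-28 days or toxicity recurs, then reduce 1 dose level".

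Section 6.2.1 (general guidelines) interrupts dosing for any grade 3 toxicity, and for intolerable or prolonged grade 2 toxicity (over 14 days). It resumes a new 28-day regimen once the event is grade 1 or lower. It sets no 28-day limit on recovery.

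**The concern.** Both columns end treatment with the same two drugs, so they ought to ask the same question of the same laboratory value. One asks whether the patient is back to his or her own baseline. The other asks whether the patient is at grade 1 or lower. A patient can satisfy the second for weeks without satisfying the first, and section 6.2.1 points to the second.

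Hepatotoxicity is a named event of special interest (section 8.1.3). Section 9.7.1 expects 3 to 12 Phase 2 patients, with PFS as a key secondary endpoint. Table 13 schedules no MRI after the end-of-treatment visit, only a safety call and survival contacts. The text a site happens to read can therefore change both a patient's exposure and how that patient's progression is ascertained.

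**Working it through.** No power, alpha or event count is involved, so there is no plan figure to reproduce. The check applies each column's rule to the same recovery path.

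**Inputs.** From Table 11: grade 2 is > 3.0 to 5.0 x ULN and grade 3 is > 5.0 to 20.0 x ULN. I infer that grade 1 runs up to 3.0 x ULN and grade 0 up to 1.0 x ULN. Days are counted from interruption, which the table does not state. The paths are illustrations, not trial data.

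**Direction of strictness.**
- Baseline grade 0 or 1 means baseline ≤ 3.0 x ULN. Any value at or below baseline is then ≤ 3.0 x ULN, that is, grade 1 or lower. Recovery to baseline cannot come before recovery to grade 1, so the everolimus stop cannot fire without the ribociclib condition also being met.
- Baseline grade 2 reverses the order. Grade 1 or lower implies baseline grade or lower, so the everolimus stop can fire alone.

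**Paths (x ULN).**

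| Row | Baseline, peak, course | Ribociclib recovery day; 28-day condition | Everolimus recovery day; 28-day condition |
|---|---|---|---|
| 0/1 to 2 | 0.8, 4.0, then 1.5 from day 10 | not reached; met | 10; not met |
| 0/1 to 2 | 2.0, 4.0, then 2.5 from day 10 | not reached; met | 10; not met |
| 0/1 to 2 | 0.8, 4.0, 1.5 on day 10, 0.8 on day 25 | 25; not met (reduction clause applies) | 10; not met |
| 0/1 to 2 | 0.8, 4.0, 1.5 on day 10, 0.8 on day 30 | 30; met (reduction clause also applies) | 10; not met |
| 0/1 to 3 | 0.8, 8.0, then 2.0 from day 14 | not reached; met, but no verb | 14; not met |
| 2 to 3 | 4.0, 8.0, then 4.0 from day 14 | 14; not met, restart | not reached; met, stop both |

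**Reading the table.**
1. *Column mismatch.* In the first two paths one column's stop fires and the other's does not. The ribociclib stop names both drugs and the coupling sentence carries everolimus with it, so the whole row gives discontinuation. The everolimus cell of this row tells the site to resume at the same dose without the condition, present in the grade 3 row, that ribociclib has been resumed. That makes it easier to misread alone.
2. *Overlap.* At day 30, 30 > 21 triggers the reduction and 30 > 28 triggers discontinuation, both inside one ribociclib cell. At day 25 only the reduction applies. Every recovery after day 28 falls under both. The bilirubin row avoids this by ending its window at day 28.
3. *Missing verb.* In the grade 0/1 to 3 row the only complete 28-day stop instruction is the everolimus one. For the path shown, section 6.2.1 would resume dosing at day 14, while the ribociclib column waits for a baseline that is not reached.
4. *True conflict.* In the grade 2 to 3 row the ribociclib column restarts at day 14 at a lower level, and the everolimus column discontinues both drugs once 28 days pass without grade 1.

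**Reach of the last row.** Section 5.2 requires ALT and AST < 2.5 x ULN in the absence of liver metastases, below the > 3.0 x ULN that defines grade 2. If baseline means screening, the row is almost unreachable. Table 11 does not define baseline.

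**Scale.** One patient is 1/12 = 8% to 1/3 = 33% of the expected Phase 2 cohort.

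**The case against.** The best defence is that a careful reader reaches one answer in the row that matters most. For grade 0 or 1 baselines the ribociclib rule is the stricter, it names both drugs in the grade 2 row, and everolimus must follow ribociclib. An everolimus stop that has not fired is not permission to restart ribociclib. Section 6.2.1 calls itself general and points to more detailed guidance; it also asks that variances go to the sponsor first. All of this stands. A reader might infer that the grade 2 row both continues and discontinues the same patient; read as a whole, it does not.

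The defence does not cover the rest. No text says that Table 11 overrides 6.2.1. The stricter-column argument has no explicit instruction to rest on where the verb is missing, and a strictest-rule reading would reverse which column governs in the grade 2 to 3 row. Treating the 28-day stop as overriding the open-ended reduction window is sensible, but it is the reader's repair.

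A reader might also infer that the liver-test schedules contradict each other. Table 11 says "Repeat liver enzymes and bilirubin tests twice weekly for 2 weeks after dose resumption". Section 6.2.3.2 says "Thereafter monitoring must be continued every 2 weeks (or more frequently if clinically indicated) for two additional cycles (e.g. 6 weeks"), and Table 12 agrees with it. These differ but are compatible. The latter two set a minimum and allow more frequent testing, they run from resolution rather than from restart, and Table 12's note refers back to Table 11. Following Table 11 satisfies both. Test frequency also has no bearing on which stop rule applies.

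**Conclusion.** The concern holds as an internal inconsistency in the stop and restart rules for AST/ALT events. It has four parts: different 28-day criteria in the two columns, with 6.2.1 resuming at grade 1 or lower; a ribociclib stop sentence without a verb in the grade 0/1 to 3 row; overlapping reduction and discontinuation windows in the grade 0/1 to 2 row; and a true cross-column conflict in the grade 2 to 3 row. The first is a risk of divergent practice between sites rather than a logical contradiction. The last is a contradiction, but rare if baseline means screening.

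The number of patients affected cannot be estimated, because the readable text gives no incidence of such events. The conclusion rests on the inferred grade 0 and grade 1 limits, on counting days from interruption, and on the missing verb being absent from the source table and not lost in text extraction. It should be corrected because it governs stopping for an event of special interest in a very small cohort. I take no view on which criterion is clinically right.

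**What to change.** For each AST/ALT row, reconcile the two columns so that the row states one recovery criterion and one action for both drugs. Specifically:

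- Make the 21-day and 28-day windows in the grade 0/1 to 2 row mutually exclusive.
- Complete the ribociclib sentence in the grade 0/1 to 3 row.
- Resolve the grade 2 to 3 row, and define baseline (screening, or start of Phase 2) and the day from which the 28 days run.
- Align section 6.2.1 with the result, or state that Table 11 takes precedence for the toxicities it lists.

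The sponsor decides which criterion and action apply. The cost is an amendment to table and section wording, with no new assessments and no change to sample size or analysis.

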Worst toxicity (CTCAE 4.03 Grade)*	Regimen Modifications for Ribociclib Management Recommendations	Regimen Modifications for Everolimus Management Recommendations
Stomatitis		
Grade 1 Minimal symptoms; normal diet	No dose adjustment required. Manage with non-alcoholic or salt water (0.9%) mouthwash several times per day	
Grade 2 Symptomatic but can eat and swallow modified diet	If everolimus is interrupted/discontinued, ribociclib should also be interrupted/discontinued. Resume ribociclib at same dose level if everolimus is resumed at same or lower dose level.	Interrupt everolimus until recovery to Grade ≤ 1. Reinitiate everolimus at same dose. If recurs at Grade 2, interrupt dose until recover to Grade ≤ 1. Resume at 50% of previous dose; change to every other day dosing if the reduced dose is lower than the lowest available strength. Manage with topical analgesic mouth treatments.
Grade 3 Symptomatic and unable to adequately eat or hydrate orally	If everolimus is interrupted/discontinued, ribociclib should also be interrupted/discontinued. Resume ribociclib at same dose level if everolimus is resumed at lower dose level.	Dose interruption of everolimus until recovery to Grade < 1. Resume at 50% of previous dose; change to every other day dosing if the reduced dose is lower than the lowest available strength.
Grade 4 Symptoms associated with life-threatening consequences	Discontinue ribociclib+everolimus	Discontinue everolimus and treat with appropriate medical therapy
Non-infectious pneumonitis		
Grade 1 Asymptomatic, radiographic findings only	No dose adjustment required. Initiate appropriate monitoring.	
Grade 2 Symptomatic but not interfering with Activities of Daily Living (ADL)	If everolimus is interrupted/discontinued, ribociclib should also be interrupted/discontinued. Resume ribociclib at same dose level if everolimus is resumed at same or lower dose.	Consider dose interruption of everolimus. Rule out infection and consider treatment with corticosteroids until symptoms improve to Grade < 1 Resume at 50% of previous dose; change to every other day dosing if the reduced dose is lower than the lowest available strength. Discontinue everolimus if failure to recover within 4 weeks.

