Grade 3 Symptomatic, interfering with ADL; Oxygen indicated	If everolimus is interrupted/discontinued, ribociclib should also be interrupted/discontinued. Resume ribociclib at same dose level if everolimus is resumed at same or lower dose.	Dose interruption of everolimus until symptoms improve to Grade < 1 Rule out infection and consider treatment with corticosteroids Resume at 50% of previous dose; change to every other day dosing if the reduced dose is lower than the lowest available strength. If toxicity recurs at Grade 3, consider discontinuation

Worst toxicity (CTCAE 4.03 Grade)*	Regimen Modifications for Ribociclib Management Recommendations	Regimen Modifications for Everolimus Management Recommendations
Grade 4 Life-threatening, ventilator support indicated	Discontinue ribociclib+everolimus	Discontinue everolimus, rule out infection, and consider treatment with corticosteroids.
Metabolic Events (hyperglycemia, dyslipidemia)		
Grade 1	If everolimus is interrupted/discontinued, ribociclib should also be interrupted/discontinued. Resume ribociclib at same dose level if everolimus is resumed at same or lower dose.	If toxicity is tolerable, no dose adjustment required. Initiate appropriate medical therapy and monitor.
Grade 2	If everolimus is interrupted/discontinued, ribociclib should also be interrupted/discontinued. Resume ribociclib at same dose level if everolimus is resumed at same or lower dose.	If toxicity is tolerable, no dose adjustment required. Manage with appropriate medical therapy and monitor.
Grade 3	If everolimus is interrupted/discontinued, ribociclib should also be interrupted/discontinued. Resume ribociclib at same dose level if everolimus is resumed at lower dose.	Dose interruption of everolimus until recovery to Grade < 1. Resume at 50% of previous dose; change to every other day dosing if the reduced dose is lower than the lowest available strength. Manage with appropriate medical therapy and monitor.
Grade 4	Discontinue ribociclib+everolimus	Discontinue everolimus and treat with appropriate medical therapy
All other adverse reactions Non-hematologic (excluding metabolic events)		
Grade 1	If everolimus is interrupted/discontinued, ribociclib should also be interrupted/discontinued. Resume ribociclib at same dose level if everolimus is resumed at same or lower dose.	If toxicity is tolerable, no dose adjustment required Initiate appropriate medical therapy and monitor.

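### Table 11 and the ribociclib ILD/pneumonitis table give conflicting ribociclib instructions for Grade 2 and Grade 3 pneumonitis, and nothing says which governs

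*Combined protocol and SAP*

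**What the plan says.** Section 6.2.3 governs dose changes after tumor resection, that is, in Phase 2.

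**Table 11, non-infectious pneumonitis.** In the Grade 2 and Grade 3 rows, ribociclib is held if everolimus is held. The ribociclib column then continues: "Resume ribociclib at same dose level if everolimus is resumed at same or lower dose". The everolimus column sets the trigger. At Grade 2 it says "Consider dose interruption of everolimus", with a stop rule: "Discontinue everolimus if failure to recover within 4 weeks". At Grade 3 it says "Dose interruption of everolimus until symptoms improve to Grade < 1", then a restart at half the previous dose.

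**Ribociclib ILD/pneumonitis table**, printed after the Table 11 footnotes. At Grade 2: "Interrupt ribociclib dose until recovery to Grade ≤1, then resume ribociclib at the next lower dose level". Its footnote adds: "An individualized benefit-risk assessment should be performed before resuming ribociclib". At Grades 3 and 4: "Discontinue ribociclib".

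**Surrounding text.** Section 6.2.1 exempts pneumonitis from its general Grade 2 and Grade 3 rules. Section 6.2.2 refers the reader to Table 11 for interruption and re-initiation and does not mention the second table.

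**The concern.** These are two current instructions for the same drug, the same event and the same grading system. At Grade 3 they cannot both be followed: one restarts ribociclib unchanged, the other ends it. At Grade 2 they differ on the restart dose and on whether a hold is required at all.

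Pneumonitis is not a marginal toxicity here. Section 8.1.3 lists it as an adverse event of special interest, and Section 1.2.2.3 lists it among the class effects of mTOR inhibitors. Table 11's Grade 3 row describes a patient for whom oxygen is indicated. A site following Table 11 to the letter could restart that patient on full-dose ribociclib, or could keep ribociclib going without interruption through a symptomatic Grade 2 case. Sites could also treat similar patients differently while each complies with the protocol.

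**Working it through.** The protocol states no figure to reproduce. The check is a grade-by-grade comparison, a search for a rule of precedence, and simple dose arithmetic.

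**1. Ribociclib instructions side by side**

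| Grade | Table 11 | ILD/pneumonitis table | Result |
|---|---|---|---|
| 1 | No dose change | No dose change | Agree |
| 2 | Hold only if everolimus is held (optional); restart at same dose | Hold until Grade ≤1; restart one level lower after a benefit-risk assessment | Conflict |
| 3 | Hold with everolimus; restart at same dose | Stop permanently | Conflict |
| 4 | Stop | Stop | Agree |

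**2. Does anything rank the two tables?**

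- Section 6.2.1: the general rules exclude pneumonitis, so they do not decide it.
- Section 6.2.1, more than one interruption: this ends ribociclib on repeat holds, but does not reach a first Grade 3 event.
- Section 6.2.1, variance: departures go first to the sponsor unless action is urgent, but the text does not say which table is the guideline being departed from.
- Section 6.2.2 and the note to Table 12: both point to Table 11 without mentioning the other table. If those pointers decided the matter, the less cautious rule would win.
- Table 9: its pneumonitis row lists only Grade 4. The general line for Grade 3 or higher non-hematologic events may make a Cycle 1 case a DLT, but that does not set the patient's ribociclib dose.
- Sections 8.1.1 and 8.2.2: attribution is recorded by drug, but neither table makes it a condition, and Table 11 has its own ribociclib column for this event.
- Section 8.5 is partly redacted, so the search covers visible text only.

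**3. Size of the difference**

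Inputs: ribociclib levels of 600, 400 and 200 mg/day (Table 10, whose footnote allows 200 mg below Level 0); Phase 2 starting doses of 400 mg at Level 0 and 600 mg at Levels 1 to 6 (Table 7); 21 ribociclib days per 28-day cycle (Section 6.1.4.1; Table 6 for Level 3). No earlier dose reduction is assumed.

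Formula: dose per cycle = daily dose × 21.

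- 600 × 21 = 12,600 mg; 400 × 21 = 8,400 mg; 200 × 21 = 4,200 mg.
- Grade 2, Levels 1 to 6: 12,600 versus 8,400 mg; 400/600 − 1 = −33%.
- Grade 2, Level 0: 8,400 versus 4,200 mg; 200/400 − 1 = −50%.
- Grade 3: 12,600 mg (8,400 mg at Level 0) versus 0 mg.

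A note under Table 11 suggests reductions of about 50%. From 600 mg that would be 300 mg, which is not a Table 10 level and would need 300/200 = 1.5 tablets. The ILD table refers to dose levels, so 400 mg is used here.

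**4. Recovery threshold**

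The ILD table lets ribociclib restart at Grade ≤1. The everolimus cells print a stricter limit: at Grade 2, "consider treatment with corticosteroids until symptoms improve to Grade < 1", and the same Grade < 1 limit at Grade 3. At residual Grade 1, ribociclib could restart while everolimus, as printed, could not. This may be a printing slip for ≤.

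**The case against.** The strongest defence is that the tables have different purposes: Table 11 for everolimus-caused pneumonitis, the second table for ribociclib-caused cases. That is a plausible intention, but the text does not say it. Both drugs are given together, so a site would often have no firm basis for choosing.

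It can also be said that Table 11 is not careless. At Grade 3 it holds everolimus until recovery, asks that infection be ruled out and corticosteroids considered, halves everolimus on restart, and ties ribociclib's return to that of everolimus. At Grade 2 a site can satisfy both tables on interruption by choosing to hold both drugs, so the unavoidable Grade 2 conflict is the restart dose. These points stand and make harm less likely. They do not remove the Grade 3 contradiction.

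Third, choosing the stricter table is a judgement, since Section 6.2.2 points to Table 11. That is fair. The reasons for the choice are that the second table is specific to ribociclib and is the more cautious rule for an adverse event of special interest.

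Finally, the scope is small, no event rate is available, and no statistical quantity changes. All of that is true. It limits how many patients could be affected, not whether the instruction should be corrected. The threshold mismatch is minor: Grade < 1 is also printed in the Grade 3 stomatitis and metabolic rows.

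**Conclusion.** The concern holds. The protocol is wrong as written: it contradicts itself on ribociclib at Grades 2 and 3 pneumonitis and agrees with itself at Grades 1 and 4. For a patient still on the starting dose, the two instructions differ by one ribociclib level after Grade 2 (a third of the dose at Levels 1 to 6, half at Level 0) and by the whole dose after Grade 3.

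This rests on the visible text, on Table 10 defining the next lower level, and on no earlier reduction. It applies only to post-resection Phase 2, for which Section 9.7.1 expects at most 3 to 12 patients. The documents give no basis for a rate of Grade 2 or 3 pneumonitis on this combination, so no number of affected patients is estimated. No effect on the recommended Phase 2 dose is asserted. It should be corrected because it is a safety instruction that sites cannot follow consistently.

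**What to change.** Amend the ribociclib column of the pneumonitis rows in Table 11:

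- **Grade 2:** keep the sentence that stops ribociclib when everolimus stops, so that the four-week failure-to-recover rule still carries over. Replace the same-dose sentence with the ILD table's Grade 2 instruction, including its benefit-risk assessment.
- **Grade 3:** replace the cell with an instruction to discontinue ribociclib.

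The minimum alternative is one sentence under Table 11 stating that, for ILD or pneumonitis, the ribociclib ILD/pneumonitis table governs ribociclib.

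Either way, the sponsor should settle two further points:

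1. Whether everolimus may continue, or restart alone at 50%, when ribociclib is held or stopped. Several other rows of Table 11 stop everolimus whenever ribociclib stops.
2. A single recovery threshold, Grade ≤1 or Grade <1, for both drugs.

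The cost is two cells or one sentence, the wording for those two points, and notification of sites. No extra patients or assessments are needed. The clinical price is that some patients will have ribociclib reduced at Grade 2, or stopped at Grade 3, earlier than Table 11 now requires.
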